2.13 Interim analysis

The early termination of the trial was due to limited enrollment and hence a limited sample size. Therefore, a futility analysis will not be conducted.

A final analysis will be performed after all participants have completed Week 36 (or discontinued prior to Week 36). Formal testing of the primary endpoint with full level alpha will be performed at the primary analysis time point.

Due to the low prevalence of cholinergic urticaria, an interim futility analysis may be conducted in case there is an obvious difference in recruitment speed in the three cohorts. In other words, this interim futility analysis would be triggered when approximately 50% of randomized participants in the cholinergic urticaria cohort have completed the Week 12 visit while 100% of randomized participants in the symptomatic dermographism and cold urticaria cohorts have completed the Week 12 visit. During this analysis, there will be no decision rules applied for the symptomatic dermographism and cold urticaria cohort. This analysis will be conducted to assess whether efficacy met a pre-specified level only for the cholinergic urticaria cohort.

Futility analysis results will be evaluated by the DMC based on calculated predictive probabilities of the primary estimand (see Section 2) for cholinergic urticaria. Details of the calculations and the associated thresholds will be described in the DMC Charter and its associated analysis plan. Additional analyses on the secondary estimand (see section 2) and safety will also be performed to assist in the futility evaluation, as planned in the DMC charter.

Additional analyses may be performed to support health authority interactions as necessary.

3 Sample Size

Symptomatic dermographism

The sample size justification is based on change from baseline in Total Fric Score and achievement of complete response in FricTest[®]4.0 at Week 12.

Cold urticaria

The sample size justification is based on change from baseline in CTT (in response to TempTest®4.0) and achievement of complete response in TempTest®4.0 at Week 12.

Cholinergic Urticaria

The sample size justification is based on change from baseline in itch NRS in response to the pulse-controlled ergometry test and achievement of complete response in itch NRS (itch NRS=0) at Week 12.

For symptomatic dermographism and cold urticaria, participants will be randomized in a 2:2:1:1 ratio to ligelizumab 72 mg q4w, ligelizumab 120 mg q4w, placebo - ligelizumab 120 mg q4w, and placebo - ligelizumab 72 mg q4w, respectively. In other words, participants are randomly assigned to ligelizumab 72 mg q4w, ligelizumab 120 mg q4w, and placebo group with a 1:1:1 ratio in the placebo-controlled period (i.e. up to Week 12). For cholinergic urticaria, participants will be randomized in a 1:1 ratio to ligelizumab 120 mg q4w and placebo- ligelizumab 120 mg q4w.

All sample size calculations were performed with SAS 9.4 PROC POWER.

Based on simulation studies, the sample sizes calculated below for each of the three CINDU cohorts are sufficient to maintain the power of overall multiple testing strategy (at least 90%) for the primary endpoint (see Section 2.1) and the first secondary endpoint (i.e. complete response rate following the FricTest®4.0 for symptomatic dermographism, complete response rate following the TempTest®4.0 for cold urticaria, and complete response rate in itch NRS following the pulse-controlled ergometry test for cholinergic urticaria) through the recycled alpha.

Data from each subtype is analyzed separately. Hence if sample size is not achieved for one of the subtypes, this will not impact the analysis for the other subtypes.

3.1.1 Primary endpoint(s)

3.1.1.1 Symptomatic Dermographism

Since two ligelizumab dose regimens will be tested versus placebo with respect to the primary endpoints (change from baseline in Total Fric Score at Week 12), the type-I-error will be split to 1.25% one-sided for each comparison.

Assuming the treatment difference in change from baseline to Week 12 in Total Fric Score is at least 1.3 in favor of the ligelizumab group, and a standard deviation of approximately 1.7, a sample size of approximate 56 participants per group and a drop-out rate of 10% provides 93.7% power to show that the primary analysis based on a two-sample t-test will be statistically significant at the one-sided 1.25% significance level (SAS 9.4, PROC POWER, difference in two sample means).

Mean changes from baseline in Total Fric Score of -0.6 (standard deviation: 1.4) in placebo group, -1.78 (standard deviation: 1.66) in omalizumab 150 mg group, and - 2.0 (standard deviation: 1.67) in omalizumab 300 mg group have been reported in Maurer et al 2017.

Table 3-1 Sensitivity of power to changes in assumptions (Symptomatic Dermographism)

True treatment difference ligelizumab vs placebo (Total Fric Score)	SD (Total Fric Score)	Power for primary endpoint (one-sided $\alpha = 1.25\%$, for N= 56 per arm)		
		With 5% drop-out rate	With 10% drop-out rate	With 15% drop-out rate
1.5	2	94.2%	92.8%	91.1%
1.3	2	85.6%	83.3%	80.7%
1.3	1.7	95.0%	93.7%	92.1%
1	1.3	95.3%	94.0%	92.5%

SD=Standard Deviations

3.1.1.2 Cold urticaria

Since two ligelizumab dose regimens will be tested versus placebo with respect to the primary endpoints (change from baseline in critical temperature thresholds (CTT) at Week 12), the type-I-error will be split to 1.25% one-sided for each comparison.

Assuming the treatment difference in change from baseline to Week 12 in CTTs is at least 10°C in favor of the ligelizumab group, and a standard deviation of approximately 8°C, a sample size of approximate 34 participants per group a drop-out rate of 10% provides >99% power to show that the primary analysis based on a t-test will be statistically significant at the one-sided 1.25% significance level (SAS 9.4, PROC POWER, difference in two sample means).

Mean changes from baseline in CTT of -0.3°C (standard deviation: 3.9°C) in placebo group, CTT of -10.6°C (standard deviation: 7.6°C) in omalizumab 150 mg group, and CTT of -10.4°C (standard deviation: 9.4°C) in omalizumab 300 mg group have been reported in Metz et al 2017.

Table 3-2 Sensitivity of power to changes in assumptions (cold urticaria)

True treatment difference ligelizumab vs placebo (°C)	SD (°C)	Power for primary endpoint (one-sided $\alpha = 1.25\%$, for N=34 per arm)		
		With 5% drop-out rate	With 10% drop-out rate	With 15% drop-out rate
11	10	98.1%	97.3%	96.2%
10	10	95.3%	93.9%	92.1%
10	9	98.3%	97.5%	96.5%
8	8	95.3%	93.9%	92.1%

SD=Standard Deviation

3.1.1.3 Cholinergic Urticaria

Assuming the treatment difference in change from baseline to Week 12 in itch NRS following the pulse-controlled ergometry test is at least 1.65 in favor of the ligelizumab 120 mg q4w group, and a standard deviation of approximately 3.0, a sample size of approximate 79 participants per group and a drop-out rate of 10% provides 90.2% power to show that the primary analysis based on a two-sample t-test will be statistically significant at the one-sided 2.5% significance level (SAS 9.4, PROC POWER, difference in two sample means).

Median pre-treatment itch VAS of 60 (25th percentile=40, 75th percentile=80) and median post-treatment itch VAS of 30 (25th percentile=20, 75th percentile=70) in the overall population after 4 doses of omalizumab 300 mg have been reported in Gastaminza et al.

Table 3-3 Sensitivity of power to changes in assumptions (cholinergic urticaria)

True treatment difference ligelizumab vs placebo (itch NRS)	SD (itch NRS)	Power for primary endpoint (one-sided $\alpha = 2.5\%$, N=79 per arm)		
		With 5% drop-out rate	With 10% drop-out rate	With 15% drop-out rate
1.5	2.5	95.5%	94.4%	93.2%
1.5	3.0	86.0%	84.1%	81.9%
1.65	3	91.7%	90.2%	88.5%
1.8	2.5	99.2%	98.9%	98.5%

SD= Standard Deviation

Table 3-4 Required sample size for different targeted statistical power (cholinergic urticaria)

True treatment difference ligelizumab vs placebo (itch NRS)	SD (itch NRS)	Targeted statistical power for primary endpoint (one-sided $\alpha = 2.5\%$)	Sample size required (%), from N=79 per arm		
			with 5% drop-out rate	with 10% drop-out rate	with 15% drop-out rate
1.65	3.0	90%	75%	79%	84%
1.65	3.0	80%	56%	59%	63%

SD=Standard Deviation

3.1.2 Secondary endpoint(s)

3.1.2.1 Symptomatic dermographism

- Complete response rate

Assuming a type-I-error of 2.5% two-sided and a complete response (negative outcome in the FricTest[®]4.0) rate of 11% in the placebo group. With approximate 56 participants per group and a drop-out rate of 10%, the power to show a complete response rate of 44% in the ligelizumab groups based on Fisher's exact test (SAS 9.4, two group Fisher's-exact test of equal proportions) is 91.5%.

Placebo-response rates of 11% (2 out of 18) have been reported in Maurer et al 2017.

The power of the all the endpoints included in the testing strategy is confirmed based on the simulation through the recycled alpha as planned. The detail simulation results will be provided in the statistical analysis plan.

3.1.2.2 Cold urticaria

- Complete response rate

Assuming a type-I-error of 2.5% two-sided and a complete response (negative outcome in the TempTest[®]4.0) rate of 5% in the placebo group. With approximate 34 participants per group and a drop-out rate of 8%, the power to show a complete response rate of 40% in the ligelizumab groups based on Fisher's exact test (SAS 9.4, two group Fisher's-exact test of equal proportions) is 81.8%.

Placebo-response rates of 0% (0 out of 12) and 5% (1 out of 20) have been reported in Metz et al 2017 and Krause et al 2013, respectively.

The power of the all the endpoints included in the testing strategy is confirmed based on the simulation through the recycled alpha as planned. The detail simulation results will be provided in the statistical analysis plan.

Cholinergic urticaria

- Complete response rate in itch NRS

For complete response in itch NRS, assuming a type-I-error of 5% two-sided and a complete response (see Section 2.2) rate of 13% in the placebo group. With approximate 79 participants per group and a drop-out rate of 10%, the power to show a complete response rate of 38% in the ligelizumab groups based on Fisher's exact test (SAS 9.4, two group Fisher's-exact test of equal proportions) is 91.1%.

In Gastaminza et al, complete response rates of 22% (2 out of 9) and 8% (1 out of 13) have been reported for placebo and omalizumab 300 mg group during the blinded treatment period, and 37.5% (6 out of 16) in the overall population in the open label treatment period

4 Change to protocol specified analyses

Due to the early termination of the trial and limited sample size no statistical analyses will be performed on any dataset. Summarization of the data will be limited to data listings and summary tables where necessary Below are specific changes to the SAP and subsequent output:

- No statistical analyses will be performed on the primary endpoints
- No statistical analyses will be performed on the secondary endpoints

[REDACTED]

- No interim analysis will be preformed
- No summary tables will be produced for efficacy

[REDACTED]

5 Appendix

5.1 Classification of study regions by country

Table 5-1 Region stratification defined by country enrollment:

Name	Study Countries
Asia	China; Korea; Malaysia; Thailand; Singapore; Vietnam; Philippines; Taiwan
Non-Asia	Other

5.2 Derivation rules for Week 12 treatment period

Week 12 treatment period cut-off date

The cutoff date for Week 12 treatment period is defined as below.

For the Placebo-Ligelizumab 72mg/120mg q4w group,

1. The first ligelizumab dosing date will be used if available;
2. Otherwise, if no ligelizumab dosing happened, then the cutoff date = min(end of study date, withdrawal of ICF date, date of death, IA cutoff date(if applicable)).

For other groups,

1. If participants complete treatment period or are still ongoing, the cutoff date is the first non-missing date of the following dates: Week 12 dosing date, Week 12 visit date, PD date of missing visit at Week 12, first dosing date + 12 weeks.
2. If participants early discontinue treatment,
 - a. If last dosing visit is less than Week 12, then the cutoff date = min(end of study date, withdrawal of ICF date, date of death, IA cutoff date(if applicable)).
 - b. If last dosing visit is great than or equal to Week 12, then the cutoff date is the first non-missing date of the following dates: Week 12 dosing date, Week 12 visit date, PD date of missing visit at Week 12, first dosing date + 12 weeks.

Adverse events summary tables:

The summary table is will be generated based on the cut-off date following the definition of “treatment period up to Week 12” in Table 2-5:

Adverse events happened at the same day with this cut-off date NOT included in “treatment period up to Week 12” tables.

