		Entire study	Ligelizumab 72 mg q4w [†] Ligelizumab 120 mg q4w Placebo- Ligelizumab 72 mg q4w [†] Placebo- Ligelizumab 120 mg q4w [†]

 • Study treatment exposure and • Safety data 	SAF	Up to Week 12*	Ligelizumab 72 mg q4w [†] Ligelizumab 120 mg q4w Placebo
	SAF	Entire Study	Ligelizumab 72 mg q4w [†] Ligelizumab 120 mg q4w Placebo- Ligelizumab 72 mg q4w [†] Placebo- Ligelizumab 120 mg q4w [†]

*Week 12 is defined as described in Appendix.

[†]Not applicable to the cholinergic urticaria cohort.

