2.4.2 Prior and concomitant therapies

For each CINDU cohort, the Safety set will be used for the analyses below. Due to the limited sample size of the safety dataset only listing will be presented for prior, concomitant, and post therapies.

Prior medications are defined as medications taken by trial subject and the use was stopped prior to first dose of study treatment. Prior medications for CINDU and non-related to CINDU will be listed.

Concomitant medications are defined as any medication given at least once between the day of first dose of study treatment and the date of the last study visit. The medications started taking prior to the first dosing and still be used on or after the first dosing date will be also counted as concomitant medications. CINDU-related background medications, CINDU related concomitant medication and non-CINDU related medications listings will be provided.

Listings for rescue medication (H1-antihistamin) will be generated

Concomitant medication and rescue listings will be provided for:

- Up to Week 12 visit (Visit 130) in the treatment period: in all the treatment groups and will include data from the placebo arm prior to (and on) transition to active treatment (transitioned to ligelizumab 72mg or ligelizumab 120mg group). If the start date is before the 12 week treatment period cut off definition, it will be counted in the listing for the 12 weeks treatment period.

Entire study period: in all the treatment groups and will include data from the placebo arm after transition to active treatment (transitioned to ligelizumab 72mg or ligelizumab 120mg group).

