2.7 Safety analyses

The following applies to each of the three cohorts (i.e., symptomatic dermographism, cold urticaria, and cholinergic urticaria) separately, and in the overall CINDU population.

For all safety analyses (i.e. AEs, laboratory data, vital signs, and ECG), the SAF will be used. All data will be included in the analysis regardless of rescue medication use.

All listings and tables will be presented by treatment group.

Treatment groups for evaluation of treatment period

The summaries for evaluation of the treatment periods will allow for comparisons of treatment groups with placebo, before treatment switch is initiated. Therefore, the safety data for the Placebo-Ligelizumab 72mg/120mg q4w group will be provided in two separate periods.

As adverse event tables will be provided for the treatment period up to Week 12 separately, the Week 12 treatment period definition is the treatment period up to Week 12 dosing date (excluding the Week 12 dosing date). For the Placebo-Ligelizumab 72mg/120mg q4w group, if the first dosing date transitioning to ligelizumab happened earlier or later than the Week 12 dosing date (e.g. Week 4 or Week 8) due to a dosing error, the placebo treatment period will be cut-off by all the information prior to the first ligelizumab dosing date. The detailed description of the Week 12 cutoff date definition is provided in the statistical analysis plan appendix.

Treatment groups for evaluation of entire study

The summaries for evaluation of entire study will include all the information following the study design treatment groups. In addition, the following combined groups may be used for safety analysis.

Table 2-3 Treatment groups for safety analysis

	Ligelizumab 72mg q4w	Ligelizumab 120mg q4w	Placebo	Transitioned to Ligelizumab 72mg/120mg q4w
Treatment Period up to Week 12 visit	Yes ^a	Yes ^a	Yes ¹	No
Entire Study	Yes	Yes	No	Yes ²

¹ The information before the treatment switching is initiated will be included. It means only the safety information from the period when participants receive placebo will be included in the analysis.

² The information after the treatment transitioned is initiated will be included. It means only the safety information from the period when participants receive ligelizumab 72mg/120mg q4w will be included in the analysis.

^a The treatment groups will be included in the summary tables include information up to Week 12 visit.

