2.7.1 Adverse events (AEs)

Treatment emergent adverse events (TEAEs) are events which started on or after the first dose of study treatment and within 16 weeks after the last study treatment, or events present prior to the first dose of study treatment but increased in severity based on preferred term within 16 weeks after the last study treatment.

TEAEs will be summarized in each cohort separately by the actually received treatment group:

- The number and exposure-adjusted incidence of subjects having any TEAE by system organ class (SOC) and preferred term (PT): For the participants in the placebo arm, adverse events after switching to ligelizumab (on or after Week 12) will be summarized separately for the treatment phase. The summary of the TEAEs up to Week 12 will include all the TEAEs up to Week 12 for all the treatment groups, including the placebo only group. The summary of the TEAEs for the entire study will be provided for all the treatment groups listed in Table 2-3.
- The number and exposure-adjusted incidence of subjects having any TEAE by severity: if a subject reported more than one adverse event with the same preferred term, the adverse event with the greatest severity will be presented. If a subject reported more than one adverse event within the same primary system organ class, the subject will be counted only once with the greatest severity at the system organ class level, where applicable.
- The number and exposure-adjusted incidence of subjects having any related TEAEs.: if a subject reported more than one adverse event with the same preferred term, the adverse event with the greatest severity will be presented. If a subject reported more than one adverse event within the same primary system organ class, the subject will be counted only once with the greatest severity at the system organ class level, where applicable.
- The number exposure-adjusted incidence of subjects having any serious treatment emergent adverse events (TESAEs), related TESAEs. The following significant adverse event will be listed - TEAEs leading to discontinuation and dose interruption, and TEAE adverse events of special interest (AESIs). For AESIs with adjudication (anaphylaxis, malignancy, CCV), separate listings will be provided based on the adjudicated results.
- A listing will be provided for safety topics of immunogenicity, COVID-19 infection, Liver Toxicity.

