2.7.1.1 Exposure-Adjusted Incidence Rate

Due to expected differences in exposure and follow-up due to varied duration of study participation between participants, adverse event incidence rates will be provided as “exposure adjusted AE incidence rates”.

The EAIR is defined as the number of subjects with a specific event divided by the total exposure-time among the subjects in the study group. That is, the EAIR is calculated as:

$EAIR = n / \sum t_i$, where n is the number of subjects having the i^{th} type event, and t_i is a subject's exposure time and defined as the shortest of the following:

- 1) time to the first episode of the i^{th} type event (if the event occurs),
- 2) duration of study treatment plus the 16-week washout period (approximately corresponding to five half-lives) after last treatment dose, or
- 3) end of the analysis period (Week 12 for the placebo period, week 36 for all safety follow-up).

The total exposure time of all subjects in a treatment group is $\sum t_i$. The EAIR is interpreted as the number of events occurring in a population per unit time. The exact Poisson 95% confidence interval for the EAIR will be provided as well, where an exact $100*(1-\alpha)\%$ confidence interval will be derived as follows (Garwood 1936, Sahai and Khurshid 1993):

- Lower confidence limit $L = \frac{0.5C_{\alpha/2,2n}}{\sum t_i}$ for $n>0$, 0 otherwise,
- Upper confidence limit $U = \frac{0.5C_{1-\alpha/2,2n+2}}{\sum t_i}$,

where $C_{\alpha,k}$ is the α th quantile of the Chi-square distribution with k degrees of freedom.

Whenever applicable, exposure adjusted incidence rates will be provided for the type as below:

1. TEAE and TESAE: Primary SOC level, PT level
2. Most frequent (at least 5% in any treatment group) TEAE: Primary SOC level, PT level

Treatment emergent AE of special interest.

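### SAP 5.2 puts no Week 12 limit on the 'up to Week 12' safety window for participants who stop dosing before Week 12, so their window runs to end of study

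*SAP*

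**What the plan says.** SAP 5.2 defines a single cut-off date for the Week 12 treatment period and applies it to the adverse event tables up to Week 12. It has four relevant branches.

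- **Ligelizumab, completed or ongoing (rule 1):** the first available of the Week 12 dosing date, the Week 12 visit date, the deviation date for a missed Week 12 visit, and first dose + 12 weeks.
- **Ligelizumab, stopped at or after the Week 12 dose (rule 2b):** the same four anchors.
- **Ligelizumab, stopped earlier (rule 2a):** "If last dosing visit is less than Week 12, then the cutoff date = min(end of study date, withdrawal of ICF date", then date of death and interim cut-off if applicable.
- **Placebo, never switched (placebo rule 2):** "Otherwise, if no ligelizumab dosing happened, then the cutoff date = min(end of study date, withdrawal of ICF date", then the same remaining terms.

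The body of the SAP describes the period differently. SAP 2.7 says "the Week 12 treatment period definition is the treatment period up to Week 12 dosing date (excluding the Week 12 dosing date", and leaves the detail to the appendix. SAP 2.7.1.1 lists, among the limits on time at risk, "end of the analysis period (Week 12 for the placebo period, week 36 for all safety follow-up". The footnote to Table 2-2 says "Week 12 is defined as described in Appendix". SAP 2.7.1 promises that "The summary of the TEAEs up to Week 12 will include all the TEAEs up to Week 12 for all the treatment groups". The medication listings in SAP 2.4.2 rely on the same date: "If the start date is before the 12 week treatment period cut off definition, it will be counted in the listing".

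**The concern.** Rules 2a and placebo rule 2 have no Week 12 term. A participant who stops after one, two or three doses and stays in follow-up therefore contributes events from beyond Week 12 to a table labelled as ending at Week 12. A completer in the same table is cut at Week 12.

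In an ordinary trial this would affect a minority. Here, SAP 1.1.2 says that all participants in treatment were discontinued and moved into follow-up, and that only 3 had completed Week 12. The early-stop branches have become the main rule. SAP section 4 drops all efficacy analyses and efficacy summary tables, so the counts and exposure-adjusted incidence rates (EAIR) of treatment-emergent adverse events are the main quantitative output left.

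Two things are at stake: whether the placebo-controlled safety tables cover the period they claim to cover, and whether the EAIR numerator and denominator refer to the same period.

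**Working it through.** The documents give no figure for this point, so there is none to reproduce. The check applies the written rules to the three possible early last doses.

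**Inputs**
- Doses before Week 12 are given at Weeks 0, 4 and 8 (SAP 1.1.2).
- The last follow-up visit falls 16 weeks after the last dose (SAP 1.1.2, follow-up period). This agrees with Protocol 9.1.1, where the discontinuation visit comes 4 weeks after the last dose and follow-up comes after it.
- An event counts as treatment-emergent up to 16 weeks after the last treatment (SAP 2.7.1).
- No interim analysis is planned (SAP sections 1 and 4), so that term drops out.
- 39 participants were enrolled at termination (SAP 1.1) and 3 had completed Week 12 (SAP 1.1.2).

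**Step 1. Window length.** Window end T = last dose + 16 weeks, assuming full follow-up with no withdrawal or death. Share after Week 12 = (T − 12)/T.

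| Last dose | T | Weeks past Week 12 | Share of window after Week 12 |
|---|---|---|---|
| Week 0 | 16 | 4 | 4/16 = 25% |
| Week 4 | 20 | 8 | 8/20 = 40% |
| Week 8 | 24 | 12 | 12/24 = 50% |

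If end of study is instead read as calendar Week 36, the cut-off moves to Week 36. The 16-week limit on treatment-emergent events still ends counting at Week 16, 20 or 24, so the adverse event tables are affected to the same extent.

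**Step 2. Number of subjects with an event.** With constant hazard λ per week (illustrative, not from the documents), the ratio to the 12-week number is [1 − exp(−λT)] / [1 − exp(−12λ)].

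| λ per week | T = 16 | T = 20 | T = 24 |
|---|---|---|---|
| 0.005 | 0.0769/0.0582 = 1.32 | 0.0952/0.0582 = 1.63 | 0.1131/0.0582 = 1.94 |
| 0.05 | 0.5507/0.4512 = 1.22 | 0.6321/0.4512 = 1.40 | 0.6988/0.4512 = 1.55 |
| rare-event limit | 16/12 = 1.33 | 20/12 = 1.67 | 24/12 = 2.00 |

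**Step 3. EAIR.** SAP 2.7.1.1 takes the shortest of time to first event, treatment duration plus 16 weeks, and end of the analysis period. That end can be read in two ways.
- *Literal Week 12.* An event after Week 12 enters the numerator, but the subject contributes at most 12 weeks at risk. Expected time at risk is [1 − exp(−12λ)]/λ, so the EAIR is overstated by the Step 2 factors.
- *Week 12 as defined in the Appendix.* Numerator and denominator match, and the ratio is 1.00 under constant hazard. If a rare event type occurs only before Week 12, the rate is diluted to 12/16 = 0.75, 12/20 = 0.60 or 12/24 = 0.50.

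On both readings the count of subjects includes events after Week 12.

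**Step 4. How many participants.** If N were dosed and the 3 Week 12 completers received that dose, (N − 3)/N fall under the uncapped rules: 17/20 = 85%, 27/30 = 90%, 36/39 = 92%. The documents do not give N.

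**The case against.** The best defence is that the appendix rule is deliberate. SAP 2.7 defers to the appendix, early stoppers have no Week 12 dosing date, and SAP 2.7 already accepts a placebo window longer than 12 weeks when a dosing error delays the switch. A placebo participant who never switches has no active-drug time to exclude. Table 2-3 has no entire-study placebo column, so a cap would leave that participant's later events without a table. EAIR was also chosen precisely because follow-up varies, and on the Appendix reading its ratio is 1.00 under constant hazard.

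Part of this stands. A special rule was needed, and late placebo events do need a place. But rule 2a applies equally to ligelizumab participants, who do have entire-study columns, so the placebo argument does not explain it. If longer windows were intended, the table label and SAP 2.7.1.1 would need changing instead. EAIR does not adjust the subject counts, and its own end point is stated in two ways.

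Other objections limit the size:
- Protocol 9.4 says that on early termination participants are to be seen promptly and handled as premature withdrawals. That could shorten windows, although SAP 1.1.2 says they entered follow-up.
- The SAP's Enrolled set requires only consent and a screening visit, so 39 may include undosed participants and 92% is an upper figure.
- Absolute numbers are small. There are 3 + 3 + 2 = 8 cohort-by-arm columns, so 39/8 is about 5 per column. If all stopped after three doses, the excess is about 5 × (0.1131 − 0.0582) = 0.3 subjects per column at 0.005/week, and 5 × (0.6988 − 0.4512) = 1.2 at 0.05/week.
- SAP 5.2 points to a Table 2-5 that is not in the available text. It may be a stale reference to Table 2-3 or a removed table. No visible text restores a cap.

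Footnote 1 to Table 2-3 ("It means only the safety information from the period when participants receive placebo will be included in the analysis") gives only weak support to the concern. Read strictly, it would also exclude off-treatment time before Week 12, and the sentence before it suggests that the aim is to exclude time after the switch.

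**Conclusion.** The concern holds. As written, SAP 5.2 gives early stoppers an 'up to Week 12' window with no Week 12 limit, which conflicts with SAP 2.7 and with the literal wording of SAP 2.7.1.1. With full follow-up the window overruns by 4, 8 or 12 weeks. Under the assumed hazards, the affected participants' counts are 1.22 to 1.94 times the 12-week number. The EAIR is either overstated by the same factors or correct under constant hazard, depending on a definition the SAP leaves ambiguous.

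The size rests on full follow-up, illustrative hazards and an unknown number dosed. Withdrawal, death, loss to follow-up or curtailed follow-up would reduce it. The rule treats the arms alike, so no direction of bias between them is claimed. The defect is a mislabelled window of unequal length and an undefined denominator. It should be fixed before the safety tables are produced.

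**What to change.** 1. In SAP 5.2, set both early-stop cut-offs (rule 2a and placebo rule 2) to the earliest of first dosing date + 12 weeks, end of study, ICF withdrawal, death and interim cut-off. The 12-week term is already used elsewhere in 5.2. Keep the first ligelizumab dosing date for placebo participants who switch.
2. In SAP 2.7.1.1, state that time at risk for the Week 12 period ends at this same cut-off.
3. State where events after Week 12 in never-switched placebo participants are reported. A flagged listing would do, as would the placebo-to-ligelizumab entire-study columns already in Table 2-2.
4. Correct or confirm the Table 2-5 reference in 5.2.

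As an optional tidy-up, apply the exclusion of events on the cut-off day only where the cut-off is a dosing date.

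With item 1, every window ends at about Week 12 (84 days after first dose) or earlier for early stoppers, in line with completers. The medication listings in SAP 2.4.2 follow automatically. The cost is SAP wording, a small programming change and one listing or footnote. No new data are needed.
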